All subjects who are ongoing in the Extension Phase Part A and who have completed at least 18 months of treatment in the Extension Phase Part A may take part in an optional Dosing Regimen substudy to evaluate the effects on safety, PK exposure, biomarker, and clinical efficacy of alternate dosing regimens for maintenance dosing of BAN2401. Subjects may choose to enter this substudy at any study visit according to their prior biweekly schedule of assessments. Subjects who participate in this substudy will be randomized to 1 of 2 intravenous dosing regimens; either BAN2401 10 mg/kg Q4W or BAN2401 10 mg/kg once Q3M. Subjects will adopt a new schedule of assessments specific to the Dosing Regimen substudy (Table 14 and Table 15). Subjects will undertake a baseline plasma blood draw upon entry to the substudy and will attend site visits Q4W, regardless of dosing regimen for the 1st year of the Dosing Regimen substudy. Blood will be drawn at each Dosing Regimen substudy visit for plasma biomarker monitoring to assess that baseline levels (at substudy entry) are maintained over the course of treatment at each dosing regimen. The sponsor will assess the plasma biomarker responses periodically, and if an optimal regimen is established, that regimen will be administered to all subjects in the substudy. For those subjects who undergo an optional amyloid PET assessment, a Dosing Regimen substudy baseline amyloid PET assessment should be conducted before substudy Visit 1 (Week 1), unless it has been conducted within 3 months of the Dosing Regimen substudy Visit 1. Subjects may participate in home infusions with sponsor and medical monitor approval, and in accordance with local guidelines. (revised per Amendments 17 and 19).

EXTENSION PHASE ASSESSMENTS

All subjects will provide informed consent and subjects will be assessed for eligibility for the Extension Phase Part A. Current medical history will be assessed at the Extension Baseline visit (Extension Screening Visit) to ensure safety in continued study participation. A complete physical examination will be performed at Extension baseline (Extension Screening Visit). Safety assessments will be performed and all AEs and SAEs recorded. Vital signs will be assessed when study drug is administered both at predose and after infusion. During Visits 44, 45, 46, and 47, vital signs should be obtained at least 2 hours after infusion. (revised per Amendment 19)

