Subjects who discontinue the study or study drug early are requested to undertake the Early Termination Visit (within 7 days after the discontinuation of study drug) and the Follow-Up Visit (3 months after the last dose of study drug). The 3-month Follow-Up Visit is not required for any subject who transitions directly from the Extension Phase (including the postmarketing section in Japan) of the study to commercial BAN2401. (revised per Amendments 18 and 19)

Every effort should be made to have the Early Termination Visit and Follow-Up Visit, conducted at the study site. However, with approval from the sponsor, subjects who cannot visit clinical sites for various reasons may have these visits performed by the home infusion staff. (revised per Amendment 17)

For those subjects who are taking part in the Dosing Regimen substudy, subjects are to contact sites between their scheduled clinic visits if there are any changes in their medical condition including new AEs and changes in medication. If for any reason study reasons are missed, the investigator should maintain close contact with the subjects (eg, via telephone) to ensure medical and safety oversight, at least every 6 weeks. (revised per Amendment 17)

Table 11 Summary of Blood Sample Volumes in the Extension Phase Part A (revised per Amendment 15 and 19)

Assessment	Total Number of Collection Timepoints	Sample Volume, Number of Timepoints x Volume per Collection (ml)	Total Volume (ml)
		Extension Phase Treatment and Follow-Up Periods	
Clinical laboratory tests	16	16 x 10 mL	160
Blood sampling for serum anti-BAN2401	16	16 x 10 mL	160
Blood sampling for serum BAN2401 PK	29	29 x 3 mL	87
Blood for exploratory biomarker analysis	12	12 x 6 mL	72
All blood samples, total volume collected			479

PK = pharmacokinetic.

Table 12 Summary of Blood Sample Volumes in the Extension Phase Part A Dosing Regimen Substudy (revised per Amendments 17 and 19)

Assessment	Total Number of Collection Timepoints	Sample Volume, Number of Timepoints x Volume per Collection (ml)	Total Volume (ml)
		Extension Phase Treatment and Follow-Up Periods	
Clinical laboratory tests	7	7 x 10 mL	70
Blood sampling for serum anti-BAN2401	22	22 x 4 mL	88
Blood sampling for serum BAN2401 PK	22	22 x 3 mL	66
Blood for exploratory biomarker analysis	22	22 x 10 mL	220
All blood samples, total volume collected			444

PK = pharmacokinetic.

STUDY DRUG SUPPLIES

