 - r For Subjects on the Q3M (3 monthly) dosing regimen, subjects do not need to attend any visits after Visit 14 (Week 53) where only Vital Signs, Prior/Concomitant Medication, and Adverse Events are scheduled.

Table 15 Dosing Regimen Substudy Schedule of Assessments – (Visits 26 through Follow-Up, Weeks 101 through 157) (revised per Amendment 17)

Phase	Dosing Regimen Substudy																	
Period	Treatment																	
Visit(s) ^a	26	27	28	29	30	31	32	33	34	35	36	37	38	39	40	Early Termination Visit ^b	Follo w-Up	Unscheduled Visit ^c
Substudy Week(s)	101	105	109	113	117	121	125	129	133	137	141	145	149	153	157			
Procedures/Assessments																		
Vital signs ^d	X	X	X	X	X	X	X	X	X	X	X	X	X	X	X	X	X	X
Weight ^e		X				X		X				X			X		X	
Routine physical exam		X						X							X	X	X	X
12-lead ECG ^f		X						X							X	X	X	X
Urine pregnancy test ^g		X				X		X				X			X	X		X
Blood for laboratory tests ^h		X						X							X	X	X	X
Urinalysis		X						X							X	X	X	X
MMSE ⁱ		X						X							X	X	X	X
CDR ⁱ		X						X							X	X	X	X
ADAS-Cog ⁱ		X						X							X	X	X	X
C-SSRS		X						X							X	X	X	X
Safety MRI ^j		X						X							X	X	X	X
Volumetric MRI ^k		X						X							X	X	X	X
Amyloid PET ^l		X													X	X		
Study drug administration Q4w ^m	X	X	X	X	X	X	X	X	X	X	X	X	X	X				
Study drug administration Q3M ^{m,n}			X			X			X			X						
Blood for serum BAN2401 PK ^o			X			X			X			X			X	X	X	X
Blood for exploratory PD biomarker analysis ^p			X			X			X			X			X	X	X	X
Blood for serum anti-BAN2401 ^q			X			X			X			X			X	X	X	X

Prior/concomitant meds	X	X	X	X	X	X	X	X	X	X	X	X	X	X	X	X	X	X	X
Adverse events	X	X	X	X	X	X	X	X	X	X	X	X	X	X	X	X	X	X	X

ADAS-Cog = Alzheimer’s Disease Assessment Scale-Cognitive subscale, C-SSRS = Columbia Suicide Severity Rating Scale, CDR = Clinical Dementia Rating, CDR-SB = Clinical Dementia Rating – Sum of Boxes, ECG = electrocardiogram, IVRS = Interactive Voice Response System, MMSE = Mini-Mental State Examination, MRI = magnetic resonance imaging, OLE = open-label Extension, PET = positron emission tomography, PD = pharmacodynamic, PK = pharmacokinetic, Q3M = every 3 months, Q4W = every 4 weeks, QTcF = corrected QT interval by Fredericia.

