- k A volumetric MRI sequence will be collected in ALL subjects immediately following all safety MRI assessments.
- l PET in this substudy is optional, but encouraged - A Dosing Regimen substudy baseline amyloid PET assessment should be conducted before substudy Visit 1 (Week 1). Those who are already participating in OLE amyloid PET substudy need not to undertake a baseline PET if they had amyloid PET with in last 3 months as a part of extension phase (at entry).
- m If approved by the Sponsor, and allowable and conducted according to country and local guidelines, subjects may be offered the option of home infusions for approved visits. If a subject begins home infusion during the Dosing Regimen substudy, subjects must be observed for at least 2 hours following the first and second home infusion by the infusion staff. After the third infusion, if no untoward effects of infusion are noted, or infusion reactions can be prevented with prophylaxis, then subjects will be observed 30 minutes after the end of infusion if judged medically stable by the infusion staff.
- n Subjects on the Q3M (3 monthly) dosing regimen do not need to attend any visits after Visit 14 (Week 53) where only Vital Signs, Prior/Concomitant Medication, and Adverse Events are scheduled.
- o If home infusion occurs at visits where PK samples are taken, blood will be taken for the BAN2401 assay only at predose.
- p Blood for serum PD should be taken predose at specified visits.
- q Blood for the BAN2401 anti-drug antibody assay will also be taken at the Early Termination Visit when applicable. At Early Termination and the Follow-Up Visit, the sample can be taken at any time.

STATISTICAL METHODS (revised per Amendments 11, 15, 16, 17, and 19)

Primary Endpoint

- Safety assessments will be based on medical review of AE reports and the results of vital sign measurements, ECG, physical examinations, clinical laboratory tests, anti-drug antibody (ADA) test results, and any relevant test of cognitive function to evaluate decline. Additionally, MRI assessments of microhemorrhage, vasogenic edema, and other clinically significant abnormalities will be evaluated.

Secondary Endpoints

- Change from baselines in brain amyloid levels as measured by amyloid PET at 3 months (Visit 50 [Extension Week 13], Cohort 1) or 6 months (Visit 57 [Extension Week 27], Cohort 2), 12 months and annually thereafter in the Extension Phase (revised per Amendment 15)

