- Change from end of Core Study in brain amyloid levels as measured by amyloid PET at the baseline of Extension Phase
- Proportion of amyloid positive subjects over time

Exploratory Endpoints

- Change from baselines in ADCOMS, CDR-SB, ADAS-Cog, and MMSE at each visit assessed
- Time to worsening of CDR global scores, eg, the worsening of global CDR score is defined as an increase from baseline by at least 0.5 points on the global CDR scale on 2 consecutive scheduled visits at which global CDR is measured
- Change from baselines in total hippocampal volume and other biomarkers annually in the Extension Phase (revised per Amendment 15)
- Describe the characteristics, comorbidities, treatments, associated costs for subjects with EAD, and study partner burden up to 5 years before study enrollment, for the duration of the Core Study, the duration of the period between the end of the Core Study and the Extension Baseline (if applicable), the duration of the Extension Phase (if applicable), and for up to 3 years after the end of the Core Study or Extension Phase (where applicable) (revised per Amendment 16)

Dosing Regimen Substudy Endpoints (revised per Amendment 17)

- Change from substudy baseline in brain amyloid levels as measured by amyloid PET
- Change from substudy baseline in plasma A β 42/40 ratio and plasma p-tau181
- Change from substudy baseline in ADCOMS, CDR-SB, ADAS-Cog, and MMSE at each visit assessed
- Safety assessments including, but not limited to, AEs, vital signs, ECG, physical examinations, clinical laboratory tests, anti-drug antibody (ADA). MRI assessments of microhemorrhage, vasogenic edema, and other clinically significant abnormalities
- Population PK parameters of BAN2401 in serum, including but not limited, to AUC, C_{av}, Correlation of PK exposure with biomarkers, safety parameters, and efficacy

ANALYSIS SETS

- The **OLE Full Analysis Set (OLE-FAS)** is the group of subjects who receive at least 1 dose of study drug during the Extension Phase and who have a baseline assessment and at least 1 postdose efficacy measurement during the Extension Phase Part A. The baseline assessment is defined as the last measurement prior to first dose of BAN2401 in the Extension Phase Part A. (revised per Amendments 17 and 19)

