Biomarker and efficacy analysis in the Dosing Regimen substudy will also be performed similarly by dosing regimen. The details will be included in SAP. (revised per Amendment 17)

Additional analyses and summaries will be performed as appropriate.

SAFETY ANALYSES

Safety analysis will be performed similarly to the Core Study. All safety analyses will be based on Safety Analysis Set of the Extension Phase. The incidence of TEAE, laboratory test variables, ECG findings, vital signs, brain MRI, ADAs will be summarized using the descriptive statistics. (See [Section 9.7.1.8](#))

Safety analysis in the Dosing Regimen substudy will also be performed similarly by dosing regimen. The details will be included in SAP. (revised per Amendment 17)

EXPLORATORY ANALYSES

No hypothesis testing will be performed for efficacy variables. Descriptive summary statistics will be generated for the efficacy endpoints as follows:

- Continuous variables will be summarized by number, mean, median, maximum, and minimum
- Categorical variables will be summarized by number and percentage

Additional summary/analyses will be performed using appropriate statistical methodologies if deemed necessary.

SAMPLE SIZE RATIONALE

There is no sample size calculation for the Extension Phase Part A. (revised per Amendment 19)

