- b: Q4W visits will occur every 4 weeks and are only applicable to those in the Dosing Regimen Substudy who are on that regimen. At any point subjects may revert to Q2W (Biweekly) infusion visits.
- c: Q3M visits will occur every 12 weeks and are only applicable to those in the Dosing Regimen Substudy who are on that regimen. At any point subjects may revert to Q2W (Biweekly) infusion visits.
- d: Subjects who discontinue study drug early or who transitions to commercial BAN2401 are requested to undertake the Early Termination Visit (within 7 days after discontinuation the last dose of study drug) and the Follow-Up Visit (3 months after the last dose of study drug). The 3-month Follow-Up visit is not required for any subject who transitions directly from the Extension Phase (including the postmarketing part in Japan) of the study to commercial BAN2401.
- e: Unscheduled visits may be conducted at any time when safety or MRI data indicates it to be necessary, per protocol or as clinically indicated in the judgment of the investigator. Note that assessments indicated under Unscheduled Visits need not always be conducted – actual assessments needed will be determined by the investigator and will be based on the specific visit needs.
- f: Subjects who completed the 5 years Extension Phase without transitioning to commercial BAN2401 are required to attend an End-of-Study Visit (Visit 174 Week 261) and a 3-month Follow-Up Visit.
- g: If approved by the Sponsor, and allowable and conducted according to country and local guidelines, subjects may be offered the option of home infusions for approved visits. If a subject begins home infusion during the dosing regimen substudy, subjects must be observed for at least 2 hours following the first and second home infusion by the infusion staff. After the third infusion, if no untoward effects of infusion are noted, or infusion reactions can be prevented with prophylaxis, then subjects will be observed 30 minutes after the end of infusion if judged medically stable by the infusion staff.
- h: Vital signs will be measured both at predose and after infusion; the timing of post dose vital signs is at investigator discretion based on prior infusion visits. Vital sign measurements will consist of systolic and diastolic blood pressure (mmHg) measured after at least 3 minutes in a semi supine position, pulse (beats per minute), respiratory rate (per minute), and body temperature (in centigrade).

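### After Week 53 of the Dosing Regimen substudy, scheduled AE queries and vital-sign readings differ by randomized regimen, so the by-regimen safety summary can under-count events in the Q3M arm

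*Protocol*

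**What the plan says.** Appendix 4 of the protocol (Dosing Regimen Substudy) randomizes consenting Extension Phase Part A subjects to 10 mg/kg Q4W or Q3M. In the first year the visit schedule is common: subjects "will attend site visits Q4W, regardless of dosing regimen for the 1st year of the Dosing Regimen substudy".

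After Visit 14 the schedules part. Table 15 footnote n, which covers Visits 26 to 40, reads: "Subjects on the Q3M (3 monthly) dosing regimen do not need to attend any visits after Visit 14 (Week 53) where only Vital Signs"; the sentence goes on to name medications and AEs. Table 14 footnote r gives the Q3M arm the same rule for the visits after Visit 14 in that table. No equivalent waiver exists for Q4W, whose subjects are dosed at every 4-weekly visit through Visit 39.

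The substudy endpoints in Appendix 4 name "Safety assessments including, but not limited to, AEs, vital signs, ECG, physical examinations, clinical laboratory tests" and further items. Under Safety Analyses: "Safety analysis in the Dosing Regimen substudy will also be performed similarly by dosing regimen", with details left to the SAP.

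Between visits, Appendix 4 (the COVID-19 and extenuating-circumstances section) says of substudy participants that "subjects are to contact sites between their scheduled clinic visits if there are any changes in their medical condition including new AEs" or in medication. The next sentence asks the investigator to keep in contact "to ensure medical and safety oversight, at least every 6 weeks". Its trigger is garbled, however: it refers to study reasons being missed, where visits or doses may be meant.

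**The concern.** Safety at less frequent dosing is a stated substudy objective, and AEs and vital signs are named endpoints. The visits that Q3M subjects may skip are exactly those whose only purpose is to collect vital signs, medications and AEs. From Week 53 the two randomized arms are therefore observed at different frequencies on endpoints whose recorded incidence depends on how often one asks or measures.

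For vital signs, a reading that was not taken cannot be recovered later. For AEs, a mild event that has passed may not be recalled up to 12 weeks on. Both effects lower the recorded count in the less-observed arm. Two arms with the same true event rates could then show fewer mild AEs and fewer subjects with an out-of-range vital sign under Q3M.

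**Working it through.** The plan gives no figure to reproduce, so the check is a visit count.

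**Inputs.** Tables 14 and 15 (visits 4 weeks apart, Visit 1 = Week 1), footnotes r and n, Table 12 (22 collection timepoints each for PK, anti-drug antibody and biomarker blood), and the protocol version dates.

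**Step 1, year 1.** Visits 1 to 14 are 4-weekly in both arms, so there is no asymmetry.

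**Step 2, Table 15 (Weeks 101 to 157).**
- Q4W attends all 15 visits.
- Q3M must attend those with other content: Visits 27, 28, 31, 33, 34, 37 and 40, which is 7. It may skip 15 − 7 = 8.
- Counted from Visit 25 (Week 97), the Q3M gaps are 8, 4, 12, 8, 4, 12 and 12 weeks, 60 in total. The longest is 12 weeks, against 4 for Q4W.
- Vital signs are taken before and after each infusion. Q4W: 14 infusion visits × 2 + 1 = 29 readings. Q3M: 4 infusion visits × 2 + 3 = 11.

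**Step 3, Table 14 (Visits 15 to 25, Weeks 57 to 97).** This depends on the blood-draw rows, which may be distorted in the text available.
- As printed there, blood is drawn at every visit to Week 97. Footnote r then excuses nobody before Week 101, and 8 of the 26 visits after Week 53 can be skipped. Total draws would be 25 + 5 = 30, which does not match Table 12.
- If draws after year 1 follow the Q3M dosing visits, the total is 14 + 3 + 5 = 22, which matches Table 12. Q3M must then attend Visits 16, 17, 20, 22 and 25 as well as the 7 above, which is 12 of 26, and may skip 14. The mean gap is 104/12 = 8.7 weeks.

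The longest gap is 12 weeks on either reading.

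**Step 4, how much of this can be reached.** The substudy entered with Amendment 17 (16 Feb 2022). Subjects still in Part A move to Part B when Amendment 19 (31 Aug 2023) is implemented. The interval is 365 + 196 = 561 days, or 80 weeks, so a subject entering on the first date would be at about substudy Week 81. Week 101 (700 days) would fall around 17 Jan 2024. Local implementation dates are not given, so these are approximate. On the Table 12 reading, Visits 15 to 21 (Weeks 57 to 81) have Q3M required at 3 of 7 (Visits 16, 17, 20); on the printed reading it is 7 of 7.

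**Step 5, illustration of AE loss.** Suppose equal true rates, no contact between visits, and recall decaying with half-life h. The share recorded over a gap of G weeks is (1 − e^(−kG))/(kG), with k = ln 2/h. Over Weeks 53 to 157 on the Table 12 reading:

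| Assumed h (weeks) | Q4W | Q3M | Ratio Q3M/Q4W |
|---|---|---|---|
| 4 | 0.721 | 0.492 | 0.68 |
| 8 | 0.845 | 0.678 | 0.80 |
| 13 | 0.901 | 0.781 | 0.87 |
| 26 | 0.949 | 0.880 | 0.93 |
| 52 | 0.974 | 0.937 | 0.96 |
| complete recall | 1.00 | 1.00 | 1.00 |

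The half-life is an assumption, and few subjects could complete this window. The table shows direction and sensitivity. It is not an estimate for this substudy.

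**The case against.** The strongest defence is that the gaps are not left uncovered. AEs are collected continuously through the last visit, so an event in a skipped interval can be reported at the next one. Subjects are told to contact the site between visits, an informant must be available, and investigator contact is required every 6 weeks when something is missed. Safety MRI, laboratory tests, ECG, physical examination and C-SSRS fall at the same roughly 6-monthly visits in both arms. The summaries are descriptive, and details are left to the SAP.

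Much of this stands, and it limits the concern to mild or transient AEs and to vital signs. It does not remove it. Continuous collection defines what is reportable, not how often it is elicited. Self-report is asked of people with early Alzheimer's disease, and informants need attend only the visits with clinical assessments. It is unclear whether the 6-weekly rule covers a permitted absence, and telephone contact yields no vital signs. Summaries of vital signs by visit are not inflated by the number of visits, but Section 9.7.1.8 also counts out-of-range values. Nor is this simply SAP detail: protocol footnotes fix the unequal collection.

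A reader might go further in three ways that the documents do not support:
- That Q3M will look safer. The bias is possible, not certain, and is absent for AEs if recall is complete.
- That the safety comparison drives the choice of maintenance regimen. Section 9.1.3 and Appendix 4 tie any optimal regimen to plasma biomarker responses.
- That the problem carries into Part B, where "Q3M visits will occur every 12 weeks and are only applicable to those in the Dosing Regimen Substudy who are on that regimen". Substudy subjects there choose whether to keep their regimen and may revert at any point, and Appendix 5 specifies no by-regimen summary.

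**Conclusion.** The concern holds in limited form. After Week 53 the two randomized regimens have different schedules for AE queries and vital signs, with gaps of up to 12 weeks against 4, while both endpoints are to be summarized by regimen. The summary can therefore under-count mild or transient AEs and out-of-range vital signs in Q3M.

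The size cannot be derived from the documents. It depends on unreported recall and contact rates, on which reading of the Table 14 blood-draw rows is right, and on how many subjects passed Week 53 by much before moving to Part B. SAEs and assessments scheduled alike in both arms are much less exposed. This is a low-cost improvement to the safety comparison, not a threat to the substudy's conclusions on biomarkers or amyloid.

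**What to change.** In Appendix 4, Safety Analyses, state that:
- the by-regimen comparison of non-serious AEs and of out-of-range vital signs rests on Weeks 1 to 53;
- vital signs after Week 53 enter the comparison only from visits required in both regimens;
- later non-serious AEs are shown separately and labelled as unequally ascertained;
- SAEs and the commonly scheduled assessments (MRI, laboratory tests, ECG, C-SSRS) are compared over the whole period.

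Separately, reconcile the 6-weekly contact sentence in Appendix 4, and its copy in the Synopsis, with footnotes r and n, so that sites can tell whether it applies to visits that a Q3M subject is excused from.

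The cost is wording only. The downside is fewer late non-serious AEs in the main comparison; they would still be reported.
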